2.6 Exclusion Criteria

1. Diagnosis of (or treatment for) bipolar disorder, post traumatic stress disorder, psychotic disorder, substance use disorder, or eating disorder within the 12 months prior to eligibility screening
2. Change in psychotropic medication (initiation or change in dose) within the 30 days prior to eligibility screening
3. Plans to initiate or change treatment (e.g., psychotherapy, psychotropic medication, and/or other psychosocial treatment) for a mental health disorder during the study intervention period (5 weeks) as determined at eligibility screening
4. Suicide attempt within the past year
5. Active suicide ideation with intent
6. Previous participation in user testing or clinical testing of Spark or SparkRx, or other previous use of SparkRx app
7. Participation in any other clinical research involving a mental health intervention or treatment within 60 days prior to eligibility screening
8. Plans to participate in any other clinical research involving a mental health intervention or treatment during the study intervention period (5 weeks) as determined at eligibility screening
9. Any condition, comorbidity, or event that, in the opinion of the investigator, will prevent the participant from adhering to the protocol or benefitting from the intervention (e.g., coercion, low level of cognitive functioning) or will prevent investigators from being able to ensure safety (e.g., will be leaving the country during study time period)
10. Having a sibling who is a past or current participant in the study

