A participant account in a secure web portal will be created with a username (user email addresses) and a temporary password. Potential participants will log in to the portal and will be instructed to change their password. In the portal, potential participants will complete two forms needed to determine eligibility: the PHQ-8 and the Medication Use Screener (see Appendix 1). Potential participants who do not meet criteria for participation based on the PHQ-8 (score < 5) or who do not wish to (or cannot) respond to the Medication Use Screener will be informed of their ineligibility and directed to mental health resources.

Participants and legal guardians (if applicable) will then be asked to verbally confirm that they meet each eligibility criterion. To ensure privacy, legal guardians will be asked to leave the room unless the participant indicates that they want their guardian present. After confirming eligibility with the participant, the legal guardian will be asked to return and confirm the eligibility of their child. Participants who report a history of suicidal ideation or self-harm urges will be prompted to complete a safety plan in collaboration with the research coordinator and/or study clinician (Appendix 5). If participants endorse active suicidal ideation with intent during this session, they will be directed to seek an emergency psychiatric evaluation for further assessment of their risk and appropriate intervention (see section 4.8.1). Participants (or legal guardians) who indicate ineligibility to participate due to any of the other eligibility criteria will be directed to alternative mental health resources and will be ineligible to continue with participation. Participants who are ineligible as a result of having an incompatible mobile device/operating system will be sent an email offering the opportunity to schedule another video session if their device/operating system changes. All eligible participants will be provided with a safety plan document and instructions for completing and using this safety plan document should it be necessary (Appendix 5). An emailed or text reminder to complete this plan may be sent following the consent session.

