Participants will be asked to indicate in weekly participant symptom checks (PSCs; see Appendix 1) or to notify the study team if their treatment for symptoms of depression or any other health condition changes during the study, or if they participate in any other treatment/intervention research study. Participants will be encouraged to follow the advice of their doctor regarding all medical decisions. Participants will be told that this is a blinded study, meaning that most of the study staff with whom they interact after randomization will not know whether they received the SparkRx app or not. They will be provided with contact information if they need to reach out for app or web portal troubleshooting, or with questions about their participation in the study.

After eligibility is confirmed, an account for legal guardians (if applicable) in the secure web portal will be created with usernames (user email addresses), and legal guardians will be provided a temporary password to log in to change their password. Participants and legal guardians (if applicable) will be directed to complete baseline assessments in the secure web portal. Upon completion of baseline assessments, participants will be randomized (1:1) to either the SparkRx condition or the eUC only condition (see descriptions below). Randomization will be stratified by participant-reported antidepressant medication status ([yes, no] from the Medication Use Screener) and participant-reported baseline PHQ depression severity (low: PHQ-8 score <15; high: PHQ-8 score ≥15). Participants will receive instructions on how to download and log into their assigned mobile app. Following randomization and app download, the session will end. Additional information will be sent to participants via email.

Following the videoconferencing session, research coordinators will contact participants' healthcare provider offices and indicate that the patient has enrolled in this research study. If information is volunteered to the research coordinator that the participant is not a patient of the healthcare provider, the participant will be contacted to provide information for an alternative healthcare provider. As participant safety may be compromised in the absence of a known U.S.-based healthcare provider, participants will be dropped from the

study if contact information for an alternative healthcare provider is not obtained.

Intervention Period

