4.8.1 Study Staff Responsibilities

If suicide ideation is endorsed at any point during the study, a safety protocol will be initiated. If participants are found to have a high suicide risk, they will be excluded from the research study and participants will be directed to appropriate local resources. A participant has high risk for suicide if they endorse ideation with a plan or intent. All safety incidents will be documented and reported to the DSMB, IRB, and FDA as needed.

If safety risks related to suicidality are identified during a study session, a brief suicide screening assessment (e.g., Self-Injurious Behavior Thoughts and Behavior Interview (SIBTI) may be conducted (Appendix 7). If there is an immediate concern for safety, the participant will be directed to go to the nearest ER or call 911/local behavioral health emergency responders. The study clinician will be alerted and triage safety risk as per the study safety protocol. The study clinician will contact the participant and emergency contact as needed, provide resources, and determine whether additional steps are necessary.

Symptom deterioration will be defined as a PHQ-8 score ≥ 15 and a ≥ 5 -point increase from baseline or a PHQ-8 score ≥ 20 at two consecutive timepoints. If a deterioration event occurs, an alert will be sent to the study team. Freeform text entered in the mobile app, PSC assessments, and deterioration alerts will be reviewed by study staff daily. Any correspondence from a study participant will also be reviewed. If a safety concern is identified (including endorsements of or thoughts of self-harm, harming others, or others are harming them), a study team member will notify a study clinician. The contacted study clinician will review all deterioration events and concerning freeform text and reach out to participants and emergency contacts if indicated, as per the study safety protocol. The Medical Expert clinician will determine the outcome of adverse events and unanticipated adverse device effects in consultation with the independent external clinician. Data about individual safety concerns, AEs, ADEs, and outcomes of clinical reachout may be securely shared with participants' healthcare provider or referring healthcare system upon written authorization by the participant and/or legal guardian as part of the informed consent process.

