Study personnel will review all data collection materials on an ongoing basis for data completeness and accuracy as well as protocol adherence. Protocol deviations and violations will be reported in accordance with IRB and FDA guidelines. In this study, a protocol violation includes but is not limited to randomization of an ineligible participant and failure to obtain informed consent/assent. A protocol deviation includes but is not limited to minor deviations from protocol that do not impact safety or efficacy and failure to keep IRB approval up to date.

A formal Data and Safety Monitoring Board (DSMB) will be assembled in accordance with NIH and NIMH criteria to ensure that the safety of study subjects is protected and that the scientific goals of the study are being met. The team assembled for the DSMB will have relevant and complementary expertise in adolescent psychiatry, clinical trial design, digital health, and statistics. Specifically, the members of the DSMB will include a child psychiatrist with expertise in depression and related disorders, a biostatistician with expertise in clinical trial design and analysis, and an expert in digital health. Importantly, none of these individuals will be involved in any other capacity with this study or have any potential conflicts of interest in study-related outcomes. Additionally, an independent unblinded, non-voting statistician will review the validity of data summarized in reports provided to the DSMB and serve as a consultant during meetings.

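### The entry criterion bars suicidal ideation only with intent, but section 4.8.1 excludes ideation with a plan or intent, so a participant with a plan who denies intent passes the first and fails the second.

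*Combined protocol and SAP*

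**What the plan says.** Three places in the combined protocol and SAP set a threshold for suicidal ideation.

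- **Section 2.6, exclusion criterion 5:** "Active suicide ideation with intent". A plan is not mentioned.
- **Section 3.1, consent and eligibility session:** "If participants endorse active suicidal ideation with intent during this session, they will be directed to seek an emergency psychiatric evaluation". The sentence ends with a reference to section 4.8.1.
- **Section 4.8.1:** "If participants are found to have a high suicide risk, they will be excluded from the research study". The next sentence defines the term: "A participant has high risk for suicide if they endorse ideation with a plan or intent". The paragraph opens with its scope: "If suicide ideation is endorsed at any point during the study, a safety protocol will be initiated".

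Two other exclusion criteria in 2.6 bear on the point. Criterion 4 bars a suicide attempt in the past year. Criterion 9 lets the investigator bar anyone whose condition would prevent safety from being ensured; it does not name a plan.

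At the session in 3.1, participants and any guardians "will then be asked to verbally confirm that they meet each eligibility criterion". A participant reporting past ideation or self-harm urges is prompted to complete a safety plan, which is not an exclusion. Baseline assessments and 1:1 randomization follow in the same session.

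**The concern.** Eligibility is confirmed by going through the listed criteria one at a time. Someone who has thought out a plan but denies intent can truthfully clear criterion 5, and the instruction specific to that session is also silent on a plan. Yet the same answer is the protocol's definition of high risk, for which exclusion is mandatory.

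Two things are at stake.

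- **Safety and consistency.** The population is aged 13 to 21 and has depressive symptoms. Coordinators working from the criteria list and coordinators who also apply 4.8.1 could reach opposite decisions about the same disclosure. A person the protocol calls high risk could be randomized and then have to be removed.
- **Classification.** Section 4.8.1 states that "a protocol violation includes but is not limited to randomization of an ineligible participant". Under 2.6 alone this participant is not ineligible; under 4.8.1 the participant should not be in the study. The text does not say which reading settles how such a case is recorded.

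**Working it through.** **Step 1: compare the rules.** There are four combinations of plan and intent among people with active ideation.

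| Plan | Intent | Criterion 5 (2.6) | Emergency evaluation (3.1) | Section 4.8.1 |
|---|---|---|---|---|
| yes | yes | excluded | yes | excluded |
| no | yes | excluded | yes | excluded |
| **yes** | **no** | **not excluded** | **not triggered** | **excluded** |
| no | no | not excluded | not triggered | not excluded |

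The rules differ on exclusion in exactly one row.

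**Step 2: does 4.8.1 reach the enrolment session?** Its scope is any point during the study. The eligibility check comes after consent has been signed, and 3.1 itself points to 4.8.1. A plan disclosed at that session therefore falls within 4.8.1 on a natural reading. However, 4.8.1 sits under data monitoring, and nothing in 2.6 tells staff to apply it as an entry criterion.

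**Step 3: does anything else close the gap?**

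- Criterion 4 concerns attempts, not plans.
- Criterion 9 could be used, but it is a matter of opinion.
- The safety-plan prompt does not exclude anyone.
- The brief suicide screen in 4.8.1 is optional.

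None of these makes plan without intent a listed entry exclusion.

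**Step 4: is there a statistical effect?** The plan's own figure comes first. A two-sample t-test with d = 0.4, two-sided alpha 0.05 and 100 per arm has noncentrality 0.4 × √(100 × 100 / 200) = 2.83 on 198 degrees of freedom. That gives power 0.804, which agrees with the stated 80%. With the planned 10% attrition, 220 × 0.9 = 198 completers and power is 0.800.

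The documents give no rate for plan without intent, so the number k of such participants randomized and later removed is purely an assumption. Taking them on top of planned attrition:

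| k (assumed) | Share of 220 | Completers | Power |
|---|---|---|---|
| 0 | 0% | 198 | 0.800 |
| 1 | 0.5% | 197 | 0.798 |
| 3 | 1.4% | 195 | 0.794 |
| 6 | 2.7% | 192 | 0.787 |

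The largest fall is 0.800 − 0.787 = 0.013. This treats a removed participant as contributing nothing. Under 4.7.1 and 4.7.2 the primary analysis is an intention-to-treat mixed model on repeated PHQ-8 scores, so scores collected before removal would still be used.

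**The case against.** The strongest reply is that the rules can be applied together. Criterion 5 sets one bar and 4.8.1 sets a further mandatory one. Because 4.8.1 covers the whole study and 3.1 refers to it, a plan disclosed at the session should lead to exclusion before randomization. If 4.8.1 is read instead as an on-study withdrawal rule, entry and withdrawal thresholds may legitimately differ. Other protections also exist: criterion 9, access to the Medical Expert on eligibility questions, a safety-plan document for every eligible participant, and a licensed provider for everyone enrolled. The prescreening form (Appendix 3), the suicide screen (Appendix 7) and the study safety protocol are not in the supplied text, so the threshold staff use in practice cannot be seen.

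Much of this stands. A reader might infer that the protocol directs high-risk participants to be randomized, or that the two rules are irreconcilable. The documents do not support that, since 4.8.1 can catch the case in time. A reader might also infer a material loss of primary outcome data. That is not supported either: there is no rate to work from, the assumed counts barely move power, and earlier PHQ-8 scores stay in the model. A plan that first arises or is first disclosed after randomization triggers 4.8.1 whatever criterion 5 says.

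The mismatch itself remains. On the combined reading, the correct decision depends on staff looking beyond the listed criteria. On the withdrawal-only reading, the protocol admits a person who already meets its removal rule, and it gives no reason for the looser entry threshold.

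**Conclusion.** The point holds as a minor inconsistency of eligibility and safety wording. Plan without intent passes the listed ideation criterion and meets the mandatory exclusion in 4.8.1; which rule prevails at entry depends on staff applying 4.8.1 or using criterion 9. The conclusion rests on the wording alone and needs no numerical assumption. The number of people affected cannot be estimated from the documents. There is no material effect on power, and no threat to the primary analysis should be read into this.

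**What to change.** 1. In 2.6, change criterion 5 to: *Active suicide ideation with a plan or intent*. Make the same change in the prescreening form (Appendix 3, not supplied) if it repeats the criterion.
2. In 3.1, add a sentence saying that anyone endorsing ideation with a plan or intent at the session is ineligible and is handled under 4.8.1.
3. Keep the existing emergency-evaluation trigger in 3.1 at ideation with intent, and let the study clinician triage plan-only cases under 4.8.1. Widening that trigger would send every plan-only case to emergency evaluation, whereas 4.8.1 directs high-risk participants to local resources and keeps the ER or 911 for immediate concern. That would change clinical triage, which this correction does not require.

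The cost is a short protocol amendment and a few more screen-outs, all of them people 4.8.1 already classes as high risk. No change to the sample size or the analysis is needed.

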2.5 Inclusion Criteria

1. 13-21 years of age
2. PHQ-8 score ≥ 5 at eligibility screening
3. English fluency and literacy (participant and legal guardian, if applicable)
4. Access to a compatible smartphone (or other device) and operating system (i.e., capable of installing the app from the Google Play or Apple App Store; list will be provided on study website [app2]) and regular internet access
5. Participant willing and able to provide informed consent/assent and have legal guardian willing and able to provide informed consent (if required)
6. Under the care of a United States (U.S.)-based licensed healthcare provider and willing and able to provide contact information for the provider and sign a HIPAA release that allows Limbix to contact provider
7. Willing and able to provide information required for study enrollment (e.g. all responses to initial PHQ-8 assessment, and current antidepressant medication status)
8. Located in the continental U.S., Hawaii, or Alaska, and not planning to leave the U.S. during the study period (through 1-month follow up assessments, up to 11 weeks after eligibility screening)

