- The **Patient Health Questionnaire (PHQ-8) Participant and Legal Guardian Proxy** is an 8-item participant-report measure for screening for depression and for establishing depression severity¹⁰⁰. The total score ranges from 0-24, with a higher score indicating greater depression symptom severity. For participants under 18, a legal guardian proxy version of the PHQ-8 will be administered to legal guardians. Clinically significant improvement is defined as a reduction in assessment score ≥ 5 ¹⁰¹. Intervention response is defined as 50% reduction in symptoms from pre- to post-intervention, and remission is defined as a score < 5 following intervention¹⁰².
- **Medication Use Screener** is a single-item screening form that asks participants to report whether or not (yes/no) they are currently taking psychotropic medication for the treatment of depression or symptoms of depression.
- **7 item Generalized Anxiety Disorder scale (GAD-7)**. The GAD-7 is a validated 7-item participant-reported assessment for generalized anxiety disorder¹⁰³. We will evaluate changes in anxiety symptoms given the high comorbidity between anxiety and depression. The total score ranges from 0-21, with a higher score indicating greater anxiety symptom severity.
- **Pediatric Quality of Life Enjoyment & Satisfaction Questionnaire (PQ-LES-Q) Participant & Legal Guardian**: A 15-item participant-reported self-administered questionnaire that captures life satisfaction over the past week¹⁰⁴. Each question is rated on a 5-point scale from 1 (Very Poor) to 5 (Very Good). The first 14 items are summed to form a total score ranging from 14-84, with higher scores indicating higher quality of life. The 15th item ("Overall, how has your life been?") is a stand-alone item. For participants under 18, a legal guardian proxy version of the PQ-LES-Q will also be administered to legal guardians.
- **Participant Symptom Check (Participant and Legal Guardian)**. Assesses legal guardian- and participant- reported negative symptoms and changes in treatment since the last check-in, using multiple choice and free-form text responses.

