4.5 Safety Outcomes

- Number of adverse events (AEs), number of participants with AEs, and rates of AEs based on

- PHQ-8-based symptom deterioration and responses to weekly PSC questionnaires (both groups)
- Number of AEs, number of participants with AEs, and rates of AEs based on in-app freeform text (SparkRx group only)
- Number of adverse device effects (ADEs), number of participants with ADEs, and rates of ADEs (SparkRx group only)

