- Probable: An event that might be due to the use of the study device. An alternative explanation is less likely - e.g., concomitant drug(s), concomitant disease(s). The relationship in time is suggestive.
- Definitely: An event that is due to the use of the study device. The event cannot be reasonably

explained by an alternative explanation - e.g., concomitant drug(s), concomitant disease(s).

Unanticipated Adverse Device Effects (UADEs, as defined in 21 CFR 812.3, also referred to as “Unanticipated Problems”): Any serious adverse effect on health or safety or any life-threatening problem or death caused by, or associated with, a device, if that effect, problem, or death was not previously identified in nature, severity, or degree of incidence in the investigational plan or application; OR any other unanticipated serious problem associated with a device that relates to the rights, safety, or welfare of subjects.

UADEs must meet all the following criteria:

- Serious (as defined above)
- Associated with the device under investigation (possibly, probably, or definitely)
- Unexpected

No serious ADEs are expected. Given that psychotherapy and psychoeducation can lead individuals to think more about their depressive symptoms, expected ADEs may include temporary clinically significant deterioration in depressive symptoms and worsening mood. Anticipated AEs, given the study population, include suicidal ideation, non-suicidal self injury ideation, non-suicidal self injury (NSSI) that does not result in medical attention, clinically significant deterioration in depressive symptoms. Anticipated serious AEs that would be seen in this population independent of the study, include active nonsuicidal self injury resulting in medical attention, suicide attempts, death by suicide, and/or inpatient hospitalization unrelated to planned hospitalization for a pre-existing condition. Serious AEs will be reported biannually to the DSMB and to the IRB per local policy and as part of annual reporting unless they meet the definition of an UADE or unanticipated problem.

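### The PHQ-8 deterioration rule in 4.8.1 cannot be met below a score of 15, so rises of 5 to 9 points in participants entering at 5 to 9 raise no PHQ-8 alert and are left out of the PHQ-8-based adverse event count

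*Combined protocol and SAP*

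**What the plan says.** The combined protocol and SAP sets the rule in 4.8.1: "Symptom deterioration will be defined as a PHQ-8 score ≥ 15 and a ≥ 5 -point increase from baseline", with a second limb of a score of at least 20 at two consecutive timepoints. The consequence follows in the same section: "If a deterioration event occurs, an alert will be sent to the study team". After that, "The contacted study clinician will review all deterioration events and concerning freeform text". No other numerical PHQ-8 definition of deterioration appears in the supplied text.

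Four other places bear on it:

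- Section 2.5 admits participants with "PHQ-8 score ≥ 5 at eligibility screening". Table 1 shows no separate participant PHQ-8 at baseline, so this score also serves as the baseline.
- Section 3.4 says "Clinically significant improvement is defined as a reduction in assessment score ≥ 5". Sections 4.1 and 4.2 use the same 5-point fall as an outcome. None of these adds a severity condition.
- Section 4.8 says "expected ADEs may include temporary clinically significant deterioration in depressive symptoms and worsening mood", and also lists clinically significant deterioration among the anticipated adverse events. It gives no number.
- Section 4.5 counts adverse events from PHQ-8-based deterioration and from weekly Participant Symptom Check (PSC) answers in both groups, and from in-app freeform text in the SparkRx group only.

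**The concern.** The rule requires severity as well as change, and the severity floor of 15 lies well above the entry floor of 5. In the lowest entry band, a rise as large as the fall the protocol treats as clinically significant does not by itself cause a clinician to look. A fall from 14 to 5 counts as benefit, while a rise from 5 to 14 is not a deterioration event. The documents give no reason for the floor.

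Two things are at stake. One is safety: in adolescents and young adults with depressive symptoms, the PHQ-8 is the one weekly measure in both arms that could raise an alert from a stated number. The other is reporting: the PHQ-8-based counts that reach the Data and Safety Monitoring Board show worsening only when it ends at 15 or more, although the protocol itself expects deterioration as a possible effect of the device.

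**Working it through.** **Step 1: which rises the rule cannot flag.** Inputs: PHQ-8 range 0 to 24 (3.4), entry at 5 or more (2.5), the two limbs in 4.8.1. Every baseline b from 5 to 24 was paired with every later score of at least b + 5, with the later score held at two consecutive timepoints, the case most favourable to an alert. The rule was read in three ways: (A) the limbs are alternatives, as punctuated; (B) a score of 15 is needed, plus either the 5-point rise or the sustained 20; (C) the two-timepoint condition governs both limbs. All three leave the same pairs unflagged:

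| Baseline | Later scores not flagged | Largest rise without an alert (14 - b) |
|---|---|---|
| 5 | 10 to 14 | 9 |
| 6 | 11 to 14 | 8 |
| 7 | 12 to 14 | 7 |
| 8 | 13 to 14 | 6 |
| 9 | 14 | 5 |

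That is 5 + 4 + 3 + 2 + 1 = 15 of the 15 + 14 + 13 + 12 + 11 = 65 possible pairs for baselines 5 to 9. These are score pairs, not participants. With the floor of 15 removed, no rise of 5 or more goes unflagged at any baseline.

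From baseline 10 upward, a rise of 5 reaches 15. Under readings A and B it is flagged at once. Under reading C a single unsustained rise would not be, so it is not certain that the gap is confined to entrants at 5 to 9.

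**Step 2: how often this might occur.** The documents give neither a baseline distribution nor an SD of change, so these inputs are assumed: change from baseline normal with mean m of -2 to 0 and SD s of 3 to 5, baselines even over 5 to 9. With a half-point continuity correction,

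P(unflagged rise | b) = Φ((14.5 - b - m)/s) - Φ((4.5 - m)/s)

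and P(rise of 5 or more) = 1 - Φ((4.5 - m)/s).

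- Lowest case, m = -2, s = 3: values for b = 5 to 9 are 0.0151, 0.0149, 0.0144, 0.0128 and 0.0089, average 0.0132. P(rise of 5 or more) = 0.0151, so 87% of such rises are unflagged.
- Highest case, m = 0, s = 5: values are 0.1553, 0.1395, 0.1173, 0.0873 and 0.0484, average 0.1095. P(rise of 5 or more) = 0.1841, so 60% are unflagged.

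At any one assessment, then, 1.3% to 11.0% of this band would show a rise of 5 or more with no PHQ-8 alert.

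**Step 3: workload of a review prompt, under readings A and B.** Assume 20% to 40% of the 220 enter at 5 to 9, which is 44 to 88 participants.

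- Five weekly assessments: 5 × 0.0132 × 44 = 2.9, up to 5 × 0.1095 × 88 = 48.2.
- Adding the post-intervention and 1-month scores in Table 1, seven in all: 7 × 0.0132 × 44 = 4.1, up to 7 × 0.1095 × 88 = about 67.

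These are expected numbers of prompts, and one participant may produce several.

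**Step 4: noise.** With no true change and an SD of change of 2 or 3, the Step 2 formula gives 0.0115 and 0.0552: about 1% to 6% of assessments in this band would prompt a review from score variation alone.

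**The case against.** The strongest reply is that this is a deliberate design choice. Requiring severity plus change is coherent, and 15 is also the stratification cut in 3.1. A participant who rises to 10 to 14 is still in the trial's low stratum, and would raise no alert had they entered at that score. Section 3.4 defines improvement only; nothing commits the protocol to treating a rise of 5 as clinically significant deterioration. All of this stands, and it is why the point is not put as an error.

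A reader might infer that these participants worsen unseen. The documents do not support that:

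- Section 4.8.1 has staff review PSC answers and freeform text daily, and review any participant correspondence, with no score floor.
- Section 7.3 says weekly responses are monitored and requires immediate contact with the PI, study clinician or Medical Expert if deterioration occurs. It states no PHQ-8 number, though it could be read as pointing back to 4.8.1.
- Section 5 lets clinicians contact participants or guardians over worsening mood.
- Guardians of minors complete weekly proxies.

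Worsening below 15 can also enter the adverse event counts through the PSC. The routes are uneven, since freeform text exists only in SparkRx and proxies only under 18. An eUC participant aged 18 to 21 still has the PSC, correspondence and the 7.3 duty. The separate safety protocol and the PSC items are not in the supplied text and may hold further triggers.

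The prevalence figures are also open to challenge. The untruncated normal allows impossible scores below 0: at mean -2 and SD 5, about 14.5% of outcomes averaged over baselines 5 to 9. They are a rough guide to workload only.

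**Conclusion.** The gap in the PHQ-8 rule is certain and needs no assumption. On every reading of 4.8.1, an entrant at 5 to 9 can rise by 5 points or more, up to 14 minus baseline, with no PHQ-8 alert and no entry in the PHQ-8-based count. How many participants this affects is unknown; the 1.3% to 11.0% per assessment rests wholly on the assumed change distribution, and it counts missed PHQ-8 alerts, not participants missed by every route.

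Three stronger conclusions might be drawn and should not be. There is no demonstrated bias between arms, because the same PHQ-8 rule applies to both. The primary outcome is unaffected. There is no conflict with 8.2, which ties informing guardians to a clinician's finding that contact is warranted and sets no PHQ-8 threshold. The point is a safety and reporting improvement worth making because it is cheap.

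**What to change.** 1. In 4.5, keep the current deterioration definition and add one line by arm: the number and percentage of participants with a rise of 5 or more from baseline in participant-reported PHQ-8 that ends below 15. This uses data already collected and leaves the existing counts unchanged.

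2. In 4.8.1, add that during the five weekly assessments a rise of 5 or more from baseline in participant-reported PHQ-8, at any score, prompts study clinician review in both arms. State that this prompt alone is not a deterioration event, and that if the clinician finds contact warranted, guardians of minors are informed as 8.2 already provides.

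The cost is one table line, one added alert condition and the extra clinician reviews: about 3 to 48 over the five weekly assessments under the assumptions above, some of them caused by noise. If the post-intervention and 1-month scores were also made to trigger, the range would be about 4 to 67. Both ranges would be larger if the two-timepoint condition is meant to govern both limbs of the existing rule, so the sponsor should state which reading is intended.
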